3C. Background of the Study: Low back pain is an extremely common cause of pain and disability. Although several structures within the spine have been identified as pain generators, the intervertebral disc is felt to account for 40-50% of chronic low back pain [3]. The most common conservative treatment options include activity restriction, medications, physical therapy, chiropractic treatment, and steroid injections. Many patients have an inadequate response to these conservative measures and progress to surgical treatment, either lumbar fusion or disc replacement. Lumbar fusion results for discogenic pain vary considerably, and disc replacement results do not appear to be significantly superior to fusion. While minor complications are relatively common with fusion surgery, catastrophic complications can occur. These complications are relatively rare. The larger issue with lumbar fusion for discogenic low back pain is the risk/benefit ratio. It is considered to be an extensive surgical procedure involving 3-6 months of recovery. Although there is evidence that it is superior to conservative care, the results are relatively modest [4,5]. In addition, it is not uncommon for patients to perceive a lack of effect or even worsening of symptoms.

The pathoanatomy of a painful intervertebral disc has been extensively studied [6,7]. The region of the disc felt to illicit pain is the outer portion of the disc, the annulus fibrosis. The annular region can develop tears or fissures in the collagen fibers. These fissures contain an ingrowth of vascularized granulation tissue along with extensive nerve endings. These changes are felt to contribute to the development and perpetuation of discogenic low back pain. [6,7].

Prior conservative treatments aimed at annular tear pathology have been attempted with heat or radiofrequency energy with disappointing results [8,9]. Others have investigated the use of methylene blue as a neurolytic agent within the disc [10,11]. These investigators published two quality clinical studies demonstrating the efficacy of intradiscal methylene blue. Unfortunately, further investigations have not produced their excellent results [12, 13].

Ultimately, the ideal treatment for pain induced by annular tears would be through direct healing of the tears themselves. Attempts are being directed toward this goal with research in areas such as stem cells, platelet-rich plasma, and specific growth factor injections [14-16].

Another therapeutic agent which could potentially promote disc regeneration is bone marrow concentrate (BMC). Bone marrow concentrate is obtained through a simple centrifugation of autologous bone marrow aspirate. Bone marrow aspirate / concentrate has been used extensively in orthopedic clinical settings to promote tissue healing [17,18]. Growth factors, cytokines and pluripotent stem cells within the aspirate are felt to be responsible for the ability of BMC to promote tissue healing in collagen based structures [19,20].

BMC has been used studied in animal and human trials in multiple non-spine orthopedic conditions [19-23]. Results have been promising. BMC has been used in spinal surgery to augment fusion with positive results [18].

Recently bone marrow concentrate has been used in the treatment of discogenic low back pain. The results of a single trial of BMC intradiscal injection for discogenic LBP have been published with 12 and 24 month follow-up [24,25]. Pettine et al. performed a prospective trial using autologous bone marrow concentrate in a single treatment into the intervertebral discs. The study included 26 patients who had at least moderate to severe low back pain with activity for 6 months and at least 3 months of non-operative treatment without significant changes in their symptoms.

Pain and function were evaluated by visual analogue scale (VAS) and Oswestry disability index (ODI) prior to the procedure and at 3, 6, 12 and 24 months post-injection. Average VAS and ODI scores demonstrated significant improvement at all time points. At the two year mark, 81% of the patients avoided surgery. Of the 21 non-surgical patients, the average decrease in pain was 71% at 2 years. The authors also compared pre-procedural MRI disc degeneration levels (Pfirman grade) to MRI findings at 12 months. No discs appeared worse and in 8 patients there was actual improvement in the degree of disc degeneration of at least 1 Pfirman grade at the level injected.

BMC appears to have an excellent safety profile. Pettine et al. reported no significant side effects from intradiscal BMC [24,25]. In addition, no significant adverse events have been attributed to this treatment in multiple animal and human studies published for a variety of orthopedic conditions [19-23, 26].

4. Inclusion/ Exclusion Criteria

4A. Inclusion/exclusion criteria

Inclusion criteria:

- Chronic low back pain greater than 6 months with low back pain component greater than leg pain component if present.
- Average pain at least 40/100 on Visual analogue Scale (VAS)

- Inadequate response to conservative care including medication, physical therapy, and/or spinal injections.
- Males and females at least 18-55 years old.
 - Rationale for age limit of 55: Based upon the study by Depalma et al. [27], at age 55 and less the predicted probability of a discogenic source of pain is higher than any other source. Beyond 55 years of age, zygapophyseal joints have a higher predictive probability. Therefore, the pre-test probability for a test for discogenic pain beyond this age is considerably lower.
- Have provided informed consent.
- If female subjects are of child-bearing potential, they must be using an acceptable form of birth control.
- Advanced imaging of MRI or CT demonstrating abnormal disc morphology.
- Presumed lumbar discogenic pain based upon either A or B below:
 - A. Positive provocative discography in accordance with SIS guidelines [28].
 - Or
 - B. Both B1 and B2
 - B1. The patient must have MRI findings suggestive of discogenic low back pain including either a high intensity zone region or type 1 or type 2 end plate Modic changes [29-31].
 - B2. Exclusion of other structures as source of pain (see below).

Rationale for not requiring discography for inclusion:

The rationale involves several factors. Although injecting the BMC at the time of discography seems most reasonable, the volume of contrast used for the discography test may reach 3ml, when performed in accordance with SIS guidelines [28]. This leaves an inadequate volume capacity to accommodate much volume of BMC. Secondly, in accordance with SIS guidelines [28] discography requires a negative control disc. Discography is invasive and may have negative detrimental effects on the disc [32]. Therefore, potential harm may exist if discography is performed. BMC is considered to be a very benign substance; it is an autologous tissue unlikely to have any detrimental effects [17, 18, 22].

Subjecting patients to two distinct intradiscal procedures (discography prior to the BMC procedure) is difficult to justify when the purpose of discography

(including injecting a normal control level) would be for qualification of an intradiscal injection of a very likely benign substance.

In summary, (as expressed in a prior study of a regenerative intradiscal treatment publication [15]), injecting the BMC at the time of discography would not allow enough volume for the BMC and performing a separate discography procedure “solely for determining the candidacy and level for the [BMC] injection could not be justified” [15].

- If clinical suspicion for facet pain is present, subjects must have had a negative investigation of zygapophysial (facet) joints as the primary source of pain to include diagnostic medial branch blocks or intra-articular facet injections or have failed radiofrequency ablation (assumed to have had 2 false positive blocks).
- If clinical suspicion for sacroiliac joint pain is present (Paraspinal pain below L5 or dominate buttocks pain), subjects must have had a negative investigation of the sacroiliac joint as the primary source of pain to include intra-articular sacroiliac injections or diagnostic S1-3 lateral branch blocks and L5 dorsal ramus block.

Exclusion criteria:

- Active moderate to severe lumbar radiculopathy
- Negative provocative discography. (Discography is not required for inclusion but prior discogram testing found to be negative excludes the patient from the trial.)
- Very severe decrease in disc height at a planned injection level. A disc height less than 1/3 expected normal disc height will be an exclusion.
 - Rationale for this disc height exclusion criteria: Requirements for 2/3 of normal disc height has become the norm for many intra-discal procedure trials which may have originated out of the intradiscal electrothermy annuloplasty trials as a requirement for device access [8-10]. The authors do not feel that moderate disc height loss should preclude needle access nor adequate chance for clinical success.
- Active infection
- Moderate to severe anemia, thrombocytopenia, or leukopenia
- Spinal fracture within the past 6 months

- Severe psychological illness
- Inability to consent to procedure due to cognitive issues
- Prior fusion at the level considered to be the source of pain
- Pregnant or breastfeeding females.
- Severe uncontrolled renal, hepatic, hematological, gastrointestinal, metabolic, endocrine, pulmonary, cardiac, or neurological disease or any medical condition which would make the subject unsuitable for this study.
- Inflammatory arthritis
- Any cancer within the past 5 years except basal cell or squamous cell skin cancer
- Intradural disc herniation
- Coagulopathy preventing spinal injection
- Inability to stop anticoagulants other than aspirin due to other medical issues
- Exceeds 30 mg morphine equivalent per day of opioid use.
- A history of alcohol or drug abuse within the past 5 years.
- Use of any investigational drug within the past 30 days.
- Low back surgery within the past 6 months.
- Steroid injection in the spine within the past 30 days.
- Any intradiscal injection other than contrast dye or anesthetic within the past 30 days.
- A known allergy or sensitivity to heparin or citrate (used for processing BMC)
- Pending litigation involving the subject's back pain.
- Central stenosis at the level to be injected with an AP diameter less than or equal to 5 mm
- Severe anaphylactic/anaphylactoid reaction to any of the medications used. (If a patient does have a mild or moderate allergy to any of the medications used in the procedure or prior anaphylactic/anaphylactoid reaction to any food or drug, they will be given prednisone 50 mg PO 13, 7, and 1 hour prior to the procedure and diphenhydramine 50mg PO 1 hour prior to the procedure.)

- In order to mitigate any economic risk, a patient without adequate medical insurance coverage for any subsequent tests or procedures deemed clinically necessary will be excluded. BMC is an autologous blood product with multiple clinical uses. Intradiscal administration should not preclude insurance coverage for any subsequent medical issues that might develop pertaining to the intradiscal injection itself or the BMC

4B. There is no gender discrimination

Pregnant women will be excluded as above.

Women of child bearing capacity will need an acceptable form of birth control.

4C. There is no racial discrimination

4D. Persons considered to be of a vulnerable population will not be included in the study.

4E. Age: 18 years – 55 years old

4F. Number of participants: 60 participants expected to be enrolled. Duration of patient enrollment is 3 years.

Power analysis:

With two treatment patients for each placebo patient, 40 treatment and 20 placebo patients will be required to achieve 80% power to detect a difference of 0.35 in the proportion of patients with successful improvement between groups with a chi-squared test at a level of significance of 0.05, assuming the proportion of patients achieving success in the control group is 0.2 (20%) This is based upon the preliminary data calculated success rate (>50% improvement in Pain) from Pettine et al. study [24] was 61%. (Our calculation differs from Pettine et al. as we included surgical patients as failures.) The 95% CI are 44-75% using an n of 40 in our proposed treatment group. The placebo rate is a very well done spinal explanatory study was 13% [33]. The placebo rate from an intradiscal study using intradiscal normal saline was 12.5% and 23.5% using hyaluronic acid (the carrier for the treatment). We therefore used the conservative estimate of a placebo response rate of 20% in this study.

5. Study design/methods/procedures

5A. Summary of research design

A total of 60 patients with randomization 2:1 ratio (treatment : control). Pain and function will be assessed using VAS and ODI. Primary outcome will be percentage of patients in the treatment group compared to the control group at 6 months categorized as a clinical success, at least 50% relief of pain. Secondary outcomes will be comparison of success rates (at least 50% pain relief) at 3 and 12 months. Other secondary outcome will be percentage of patients in the treatment group vs control group with greater than 30% improvement in ODI at 3, 6, and 12

months. Global Perceived Effect (GPE) will also serve as a secondary out come at 3, 6, and 12 months. Medication log and adjunctive treatments will also be recorded and analyzed.

| Randomization process: computer randomization program

Randomization shall be performed through a computer randomization program.

<https://www.random.org/#numbers> (Randomness and Integrity Services Ltd. Dublin, IR.) A random number shall be generated between 1 and 60. For all randomly generated number from 1 to 40, the patient will be assigned to the treatment group. For all randomly generated random number from 41 to 60, the patient shall be assigned to the placebo group.

The patients will be blinded to treatment assignment. The patient will follow up for assessment with an investigator who remains blinded to the treatment assignment. Only the physician performing the procedure will be aware of the group assignment.

Based upon previous recommendations for the assessment of blinding success in clinical trials [34] the patients will be queried at 2 weeks whether they believe they have received the active treatment, the placebo, or if they do not know to which group they were assigned.

Treatment: a single intradiscal injection of autologous bone marrow concentrate into suspected painful discs based upon history, image findings and the exclusion of other anatomic structural sources of pain such as z-joints and SIJ.

Placebo: Intramuscular injection of normal saline directly above the transverse process at each suspected discogenic pain level. (The physician performing the procedure will not be blinded, but the assessor for follow up evaluation will be blinded).

A sham bone marrow aspiration will also be performed involving fluoroscopic guidance and anesthetic to the iliac crest. The patient will hear the noise of the bone marrow drill (unattached), while a 21 gauge needle is tapped against the periosteum.

Patients will be screened from a pool of existing patients at a community outpatient spine and musculoskeletal practice. These patients will have had an inadequate response to conservative treatments, some of whom will be considering fusion surgery. Some of these patients will be considering provocative discography through the recommendation of a local surgeon. One of the options discussed will be bone marrow concentrate intradiscal injection under the context of the study. If the patient has any interest in participating in this study, the general risks, benefits and literature will be discussed. The patient will be informed that their status as a patient in the principle investigator's practice and the physician-patient relationship will not be altered regardless of their participation in the study. They will be given a written summary of the study. If they have continued interest, an appointment will be arranged for the verbal and written consent process. Once the consent form process has been completed, the patient will perform the VAS as well as the ODI which will serve as the baseline measurement data [35]. A pain medication query shall be performed as well.

All procedures will be performed by two of the investigators ([name]). Both are board certified in Physical Medicine and Rehabilitation, experienced discographers, fellowship trained in spine injections and serve as instructors for spinal injection procedures at the national level (Spine Intervention Society). Both investigators have supplemental training and years of experience with bone marrow aspiration procedures.

Bone marrow aspiration and intradiscal BMC injection procedure:

Pre-procedure:

The patient will be offered a P.O. sedative of diazepam 5 to 10 mg or alprazolam 0.5 to 2 mg to be taken 30-60 minutes prior to the procedure. Alternatively, patients will be offered conscious sedation in the form of 2 mg to 6 mg midazolam IV with the possible addition of 50 to 150 mcg fentanyl IV. Alternatively, 50-100 mcg fentanyl may be injected IM for pain control.

Continuous cardiac, pulse oximetry, and clinical monitoring will be performed throughout the procedure. Oxygen by nasal cannula 2 to 4 L may also be used. Emergency equipment will be immediately available. The investigators ([name]) performing the procedure are ACLS certified by the American Heart Association. Conscious sedation, if utilized, will be performed in accordance with state requirements including the assistance of a nurse, physician's assistant or a second physician.

Bone marrow aspiration procedure: The patient will be placed in a prone position in our outpatient fluoroscopy suite. Strict sterile technique will be observed. The lower back will be cleansed with a solution of chlorhexadine mixed with alcohol and covered with a sterile drape.

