The data from the pre and post VAS (0-100 mm) and Oswestry disability index 0-100 will be analyzed from baseline to 3, 6, and 12 months [35]. Categorical data will be used. Primary outcome for success will be considered at least 50% improvement in pain by VAS at 6 months and secondary outcome at 3 and 12 months. Additional secondary outcomes will include 3, 6, and 12 month minimum of 30% improvement in ODI. Further secondary outcomes will also include a minimum of 30%, and 70% improvement in pain at 3, 6, and 12 months. All time point categorical success rates will be compared to placebo group with 95% CI determined. Group data mean pain scores will also be analyzed for each time point using *t*-tests. Global perceived effect will be analyzed for 3,6,12 months on a 5 point scale using categorical data analysis.

Pain medication log at baseline, 3, 6, and 12 months will be analyzed by a simple categorical decrease, increase, or unchanged compared to baseline. Morphine equivalents will not likely be helpful as the majority of the subjects will not likely be on opiate medication. Those patients not on medication at baseline shall not be included in the medication analysis.

Adjunctive treatments: All other therapeutic treatments for LBP during the study period shall be recorded at 3, 6 and 12 months.

5C. Monitoring:

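### The stated 80% power for 40 vs 20 patients works out at about 76% (formula) to 78% (exact) for a two-sided chi-squared test, with no allowance for loss

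*Combined protocol and SAP*

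**What the plan says.** The power analysis in section 4F states that "40 treatment and 20 placebo patients will be required to achieve 80% power to detect a difference of 0.35" in success proportions. The test is specified as "with a chi-squared test at a level of significance of 0.05", and control success is taken as 20%, so the design alternative is 55% vs 20%. Whether the test is one- or two-sided is not stated.

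Section 4F also says "60 participants expected to be enrolled", and 5A randomises the same total 2:1. The primary endpoint in 5A is the proportion "at 6 months categorized as a clinical success, at least 50% relief of pain".

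The analysis section, 5B, says "All time point categorical success rates will be compared to placebo group with 95% CI determined". It names t-tests for mean pain scores but no test for the success rates; the chi-squared test appears only in the power statement. No section gives a dropout rate, an inflation of the sample size, a replacement rule, or a rule for patients missing at 6 months. The remark in 4F about counting surgical patients as failures concerns the recalculation of the earlier published study, not this trial.

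**The concern.** Apart from sidedness, 4F supplies everything needed to recompute its power figure, and the recomputation does not return 80% under the ordinary reading of the named test. A reader of 4F would take the trial to have a one-in-five chance of missing a true 0.35 difference. On the plan's own inputs the chance is between 22% and 24%.

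Two features make the stated figure more fragile. The number to be enrolled equals the number said to be required, so the calculation holds only if all 60 patients are evaluable at 6 months. And because 5B does not repeat the test, the power actually obtained depends on a later choice between the uncorrected chi-squared test, its continuity-corrected form and Fisher's exact test. With 20 controls and about 4 expected control successes (20 × 0.20), those three differ noticeably.

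**Working it through.** **Inputs, all from 4F unless noted.** Treatment n = 40; control n = 20; control rate 0.20; difference 0.35, so treatment rate 0.20 + 0.35 = 0.55; level 0.05; chi-squared test; stated power 80%. *Assumption:* two-sided, critical value 1.96.

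**Step 1: the plan's figure by the pooled-variance formula** (the normal form of the Pearson chi-squared test).

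- Pooled rate = (40 × 0.55 + 20 × 0.20) / 60 = 26/60 = 0.4333
- SE under no difference = √[0.4333 × 0.5667 × (1/40 + 1/20)] = 0.1357
- SE under the alternative = √[0.55 × 0.45/40 + 0.20 × 0.80/20] = 0.1191
- Power = Φ[(0.35 − 1.96 × 0.1357) / 0.1191] = **0.760**

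**Step 2: exact power.** Summing the binomial probabilities of all 21 × 41 possible outcomes in which the uncorrected Pearson statistic exceeds 3.841 gives **0.777**.

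**Step 3: can another reading give 80%?**

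| Test, 40 vs 20, 55% vs 20% | Power |
|---|---|
| Pearson, two-sided, pooled formula | 76.0% |
| Pearson, two-sided, exact | 77.7% |
| Arcsine formula, two-sided | 77.5% |
| Fisher, two-sided, exact | 70.1% |
| Continuity-corrected, two-sided, exact | 64.7% |
| Unpooled Wald, two-sided, formula / exact | 83.6% / 81.0% |
| Pearson, one-sided 0.05, pooled formula / exact | 85.6% / 86.8% |

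The two-sided chi-squared test falls short and the uncorrected one-sided version overshoots. Only the exact power of an unpooled Wald test comes within 2 points of 80%.

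**Step 4: what would give 80%.** At 40/20 with a 20% control rate, the difference needed is about 0.360 (exact) or 0.367 (pooled formula). At a difference of 0.35 (pooled formula / exact):

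- 42/21: 78.2% / 80.7%
- 44/22: 80.2% / 79.5%
- 46/23: 82.1% / 82.2%

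Exact power does not rise steadily with n because the test is discrete.

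**Step 5: loss.** The documents give no rate, so these are assumed (pooled formula / exact Pearson):

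| Assumed loss | Handling | Power |
|---|---|---|
| 5% (38/19) | excluded | 73.6% / 74.2% |
| 10% (36/18) | excluded | 71.0% / 70.4% |
| 10% (40/20; rates 0.9 × 0.55 = 49.5% and 0.9 × 0.20 = 18%) | counted as failures | 67.6% / 69.9% |

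**Step 6: sensitivity to the other rates cited in 4F**, full 40/20, two-sided. Those are 61% for treatment, 13% for placebo in a spinal study, and 12.5% (saline) and 23.5% (hyaluronic acid) for placebo in an intradiscal study.

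| Treatment vs control | Formula / exact |
|---|---|
| 55% vs 23.5% | 65.2% / 67.5% |
| 58.5% vs 23.5% (0.35 kept) | 74.8% / 76.7% |
| 48% vs 13% (0.35 kept) | 80.0% / 82.1% |
| 61% vs 23.5% | 80.9% / 82.3% |
| 61% vs 20% | 88.5% / 89.2% |
| 55% vs 13% | 92.4% / 92.9% |
| 55% vs 12.5% | 93.2% / 93.6% |

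The 23.5% rate comes from hyaluronic acid, whereas this trial's placebo is saline.

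**The case against.** The strongest reply is that the gap is immaterial. Exact power is only 2.3 points short, a difference of 0.36 instead of 0.35 would close it, and both rates are planning guesses: 4F itself gives a 44–75% interval around the 61% anchor. The plan also chose 55%, below that anchor, and a 20% placebo rate above two of the three it cites; most of those alternatives put power above 80%. This stands as a reason to treat the matter as a correction rather than a design failure. It does not make the sentence right, since 20% and 0.35 are the values the plan attached its 80% to.

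Second, sidedness and variance form are unstated, so an unpooled calculation (81.0% exact) cannot be ruled out. That is true, but it is not the chi-squared test named, and its exact type I error is about 6.7% at a common rate of 20%.

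Third, the loss rates are not the plan's, patients come mainly from an existing practice, and they are paid for the 3, 6 and 12 month visits. These facts may help retention; they do not supply an allowance. The loss figures show sensitivity and must be labelled as assumed.

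Fourth, in a combined protocol and SAP, naming chi-squared in 4F arguably fixes the test already. This is fair: repeating it in 5B is good practice and would not justify a finding alone. The Fisher and continuity-corrected figures describe choices the plan has not made.

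**Conclusion.** The concern holds. On the plan's own inputs, a two-sided chi-squared test at 0.05 with 40 vs 20 evaluable patients has about 76% power by formula and 78% exactly, against the stated 80%. The conclusion assumes a two-sided test and a realised split of exactly 40/20. The shortfall is 2 to 4 points before any loss; an assumed 10% loss takes power to roughly 70–71% if those patients are excluded, or 68–70% if they count as failures. No version of the named test that was tried gives 80%. The power statement should be corrected, but the error is modest and does not call the trial's design into question.

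**What to change.** Keep the sample size at 60 and replace the power sentence in 4F with, for example:

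> *With 40 treatment and 20 placebo evaluable patients, power is about 76% (exact 78%) to detect 55% vs 20% success using an uncorrected chi-squared test at two-sided 0.05. If 10% of patients are assumed not evaluable and are excluded, power is about 70–71%.*

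In 5B, name the uncorrected Pearson chi-squared test, two-sided 0.05, for the 6-month primary comparison, so that analysis and power statement agree. If a sensitivity range based on the cited rates is added, label it as such and show the cases above 80% as well as those below, including the saline rate of 12.5%.

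**Cost:** wording only. The stated power becomes slightly less favourable. Naming the uncorrected test means accepting an exact type I error of 4.7% at a common rate of 20%, and at most about 5.5% (at a common rate of 50%). The rewording discloses the effect of loss but does not add an allowance for it.
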